at 4 weeks (± 2 weeks) and 12 months (± 2 months) will occur either in person or using Cleveland Clinic platform for virtual visits. In the instances where a subject cannot attend to their 1-year follow-up visit in person or through a virtual visit, information will be collected through a telephone contact. Pain intensity at different time points will be assessed using the NIH PROMIS Pain Intensity 3A scale, which is collected for all patients entered into the AHSQC. Patient quality of life and functional mobility will be assessed using the Hernia Quality of Life (HerQLes), which is also collected as standard for all patients entered into the AHSQC. Patients will be required to complete these forms at each clinic visit to allow for monitoring of postoperative progression and overall effect of heavyweight versus medium weight mesh on patient quality of life. Hernia recurrence will be assessed using the Ventral Hernia Recurrence Inventory, a validated questionnaire that can be performed either in person or via email or phone correspondence.⁸ At the time of the one month and one-year follow-up clinic visits, a routine physical examination will be performed on all patients. Confirmation of a recurrent hernia will occur if the patient reports recurrence of a bulge or hernia at the site of previous repair during the Ventral Hernia Recurrence Inventory questionnaire. If the surgeon's physical examination does not correlate with the patient-report hernia recurrence, an ultrasound or computed tomography scan will be ordered based on the usual practice of the surgeon. At the completion of the study protocol, patients will be informed as to the type of mesh that was used during the surgical operation. An additional question ("Do you feel your mesh?") will be asked to the subjects during the 1-year follow-up contact and this information will be stored in REDCap.

OUTCOMES TO BE INVESTIGATED

Each outcome to be investigated is based on the specific aims of the study and are listed below:

Version #: 6

Date Submitted: May 29, 2018

NCT03082391

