Specific Aim #1: To determine if the use of a medium weight material leads to a decrease in pain intensity at one year following surgery. This will be assessed with the use of the NIH PROMIS 3a Pain Scale. The change in scaled score one year after operation will be calculated by comparison to the scaled score obtained at baseline for each patient. The mean change at one year will be compared for each group (heavyweight mesh and medium weight mesh).

Specific Aim #2: To determine if there is a difference in ventral hernia recurrence at one year following surgery. Hernia recurrence will be determined using the Ventral Hernia Recurrence Inventory, a validated questionnaire using patient-reported outcomes to determine hernia recurrence after repair.⁸

Specific Aim #3: To determine if there is a difference in the rate of deep surgical site infection at 30-days following surgery between the two mesh types. Definitions of wound events are per the Centers for Disease Control and were agreed upon by all participating surgeons. These wound outcomes will be recorded in the AHSQC database at 30 days as follows:

Deep Incisional SSI

A **deep incisional SSI** must meet the following criteria:

Infection occurs within 30 days after the operative procedure AND the infection involves deep soft tissues (e.g., fascial and muscle layers) of the incision AND patient has at least ONE of the following:

- a. purulent drainage from the deep incision but not from the organ/space component of the surgical site

Version #: 6

Date Submitted: May 29, 2018

NCT03082391

- b. a deep incision spontaneously dehisces or is deliberately opened by a surgeon AND is culture-positive or not cultured AND the patient has at least one of the following signs or symptoms: fever ($>38^{\circ}\text{C}$), or localized pain, or tenderness. A culture-negative finding does not meet this criterion.
- c. an abscess or other evidence of infection involving the deep incision is found on direct examination, during invasive procedure, or by histopathologic examination or imaging test.
- d. diagnosis of a deep incisional SSI by a surgeon or attending physician.

NOTE:

- a. Classify an infection that involves both superficial and deep incision sites as a deep incisional SSI.
- b. Classify infection that involves superficial incisional, deep incisional, and organ/space sites as deep incisional SSI. This is considered a complication of the incision.

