The primary outcome measure of this study is the change in NIH PROMIS Pain Intensity Scale 3a scaled score one year after operation. The mean scaled score change at one year will be compared for each group (heavy weight mesh versus medium weight mesh). Patient reported outcomes within the AHSQC were evaluated for patients undergoing ventral hernia repair from July 2013 through August 2016. Twenty-three patients met criteria for medium weight mesh as defined in Table 1 and six patients meeting criteria for heavy weight mesh. Scaled score changes at one year after operation are summarized as below:

	Size	Mean	SD	Min	Lower Quartile	Median	Upper Quartile	Max
Medium weight (Group 1)	23	-10.3	10.9	30.7	41.9	46.3	53.3	71.8
Heavy weight (Group 2)	6	-7.5	6.3	30.7	41.7	47.8	53.2	54.5

Version #: 6

Date Submitted: May 29, 2018

NCT03082391

Using a two sample t-test allowing for unequal variance with equal sample sizes (1:1) group allocation of medium weight and heavyweight mesh, 160 patients per group will achieve a target power of 80% given an alpha of 0.05. Assuming a 10% loss to follow up at 1 year, a total of 352 patients will be recruited for this study (176 patients in each group).

STATISTICAL ANALYSIS

Categorical variables will be examined using Pearson's Chi-Square and all continuous variables will be examined using the non-parametric Wilcoxon signed rank test. The categorical variables will be reported using proportions and continuous variables will be reported using the median and the interquartile range.

Specific Aim 1: The Wilcoxon signed rank test will be performed to determine if the change from baseline to one-year follow-up is statistically significantly different between the medium weight and heavyweight mesh groups.

Specific Aim 2: The proportion of patients in each group reporting a hernia recurrence will be examined using Pearson's Chi-Square test to determine if there is a difference between the groups.

Specific Aim 3: The counts of the surgical site infections will be compared using Pearson's Chi-Square test to determine if an association exists between either type of mesh and frequency of SSI.

Specific Aim 4: The change in the HerQLes will be examined using the Wilcoxon signed rank test to determine if there is a difference in the quality of life after hernia repair for patients receiving medium weight vs heavyweight mesh.

Version #: 6

Date Submitted: May 29, 2018

NCT03082391

DATA SAFETY MONITORING BOARD

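### Aim 1 tests an unadjusted change score that needs both a baseline and a one-year value; a repeated-measures model adjusted for baseline and site would be more precise and would guard against some pain-related loss, using data already collected

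*Combined protocol and SAP*

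**What the plan says.** - **Outcome.** POWER CALCULATION: "The primary outcome measure of this study is the change in NIH PROMIS Pain Intensity Scale 3a scaled score one year after operation". OUTCOMES TO BE INVESTIGATED, Specific Aim #1, describes how it is formed: "The change in scaled score one year after operation will be calculated by comparison to the scaled score obtained at baseline for each patient". Group means of this change are then to be compared.
- **Test.** In STATISTICAL ANALYSIS, the entry for Aim 1 uses a Wilcoxon signed rank procedure, with this purpose: "to determine if the change from baseline to one-year follow-up is statistically significantly different between the medium weight and heavyweight mesh groups". No covariate, site term, analysis population, missing-data rule or sensitivity analysis is given.
- **Data collected.** STUDY DESIGN places follow-up "at 4 weeks (± 2 weeks) and 12 months (± 2 months) will occur either in person" or by virtual visit, with telephone contact if the one-year visit is missed. It adds: "Pain intensity at different time points will be assessed using the NIH PROMIS Pain Intensity 3A scale, which is collected for all patients". It also says: "Patients will be required to complete these forms at each clinic visit". A 4-week pain score is therefore planned, but no stated analysis uses it.
- **Loss.** The only statement is in POWER CALCULATION: "Assuming a 10% loss to follow up at 1 year", used to raise 160 per group to 176.
- **Randomization.** SURGICAL PROCEDURE describes a blocked scheme run separately at each institution.

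**The concern.** A patient without a one-year score has no change value and cannot enter the test as written, even if a baseline and a 4-week score are on file. The outcome is pain, and pain may influence who returns. The planned difference is only 2.8 points, so a modest distortion could matter.

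Separately, an unadjusted change score is an inefficient use of the baseline measurement, and the analysis ignores the site blocking used in the design. Both can be remedied with data the registry already holds.

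**Working it through.** **1. The plan's sample size.** Inputs from POWER CALCULATION: mean change −10.3 (SD 10.9) for medium weight and −7.5 (SD 6.3) for heavyweight, so the difference (heavyweight minus medium weight) is 2.8. With two-sided alpha 0.05 and 80% power:

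n = (1.960 + 0.842)² × (10.9² + 6.3²) / 2.8² ≈ 159 per group.

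The unequal-variance t-test gives 80.0% power at 160, so the stated figure reproduces. It counts only patients with a one-year change. After 10% loss, 176 × 0.9 = 158.4 per arm remain, with power about 79.6%.

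**2. When loss related to 4-week pain biases the contrast.** Assume the log odds of loss rise by b per SD of the 4-week score, the average loss is p, the score SD is s, and the 4-week and one-year changes correlate at ρ. The mean one-year change among retained patients in an arm then shifts by about

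−ρ × s × b × p.

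The bias is the difference between the two arms' shifts, so it cancels when the arms match. Large-sample simulations (1–2 million patients per arm, true difference 2.8, ρ from 0.3 to 0.7) gave:

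| Assumed pattern of loss | Bias at 10% loss | Bias at 20% loss |
|---|---|---|
| Same rule, equal SDs, no early arm difference | about 0 | about 0 |
| Same rule (odds ratio 2 per SD), equal SDs, early difference 2.8–5 points | −0.03 to −0.16 | −0.05 to −0.21 |
| Same rule per point, the plan's SDs 10.9 and 6.3 | +0.17 to +0.46 | +0.29 to +0.83 |
| Pain drives loss in the heavyweight arm only (odds ratio 2–3 per SD) | −0.18 to −0.61 | −0.32 to −1.14 |

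Hand checks at ρ = 0.5 and p = 0.1:
- Heavyweight arm only, odds ratio 2, SD 8.9: 0.5 × 8.9 × 0.693 × 0.1 = 0.31 (simulated 0.32).
- Plan's SDs, same rule of 0.693/8.9 = 0.0779 per point: 0.5 × 0.0779 × 0.1 × (10.9² − 6.3²) = 0.31 (simulated 0.32, with the opposite sign).

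If pain promotes loss in one arm and retention in the other, the bias at 10% loss reaches −0.36 to −1.23. That is an extreme assumption and is left out of the working range.

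An estimate using the 4-week score stayed at about 2.8 throughout, but only because loss was made to depend on that score.

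For scale: with the plan's SDs and 158 per arm, an expected difference of 2.5 in place of 2.8 has about 70% power.

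**3. Precision from the 4-week score.** Effective n = observed n / (1 − p × ρ²). At 10% loss, 158.4 becomes 159.8, 162.5 and 166.6 for ρ of 0.3, 0.5 and 0.7, with power 80.0%, 80.6% and 81.6%. A separate simulation of 3,000 trials assumed SD 9 and correlations of 0.4 (baseline to 12 months), 0.3 (baseline to 4 weeks) and 0.5 (4 weeks to 12 months). The standard error was 1.09 for the change score, 0.92 with baseline adjustment, and 0.91 with the 4-week score added.

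**4. Precision from baseline adjustment.** Assume equal baseline and one-year spread σ within an arm and correlation r between them. The change score has variance 2σ²(1 − r) and the baseline-adjusted score has σ²(1 − r²), so the ratio is (1 + r)/2. The unadjusted standard error at 158 per arm is √((10.9² + 6.3²)/158) = 1.002. Multiplying by √((1 + r)/2):

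| r | Ratio | SE | Power |
|---|---|---|---|
| unadjusted | 1 | 1.002 | 79.5% |
| 0.8 | 0.90 | 0.950 | 84% |
| 0.5 | 0.75 | 0.867 | 90% |
| 0.3 | 0.65 | 0.808 | 93% |

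**The case against.** The strongest reply is that the documents give no sign that loss will work differently in the two arms. Patients are told their mesh type only when the study protocol is complete, which closes one route to differential loss. Virtual visits and telephone contact should hold loss down. At 10% loss most assumed patterns move the estimate by well under half a standard error. All of this stands. A reader might infer that pain-related loss will bias the mesh effect, or will bias it toward zero. Neither is supported: with matching arms the bias is about nil, and with the plan's own unequal SDs it inflates the difference. The heavyweight SD itself rests on six patients.

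It is also fair that the plan never calls its analysis complete-case. That follows from the change-score test and the silence on missing data, and a rank test after multiple imputation would be another way to fill the gap. Patients lost by one year may also have missed the 4-week visit, for which no telephone fallback is stated.

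Finally, baseline-adjusted analysis of covariance would deliver most of the precision gain without the 4-week score. That is true. What the repeated-measures model adds is mainly protection against loss that depends on 4-week pain.

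None of this defends leaving out baseline and site, or leaving missing one-year scores without a plan.

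**Conclusion.** The point holds as a recommended improvement. As written, Aim 1 can use only patients with both scores, and it leaves baseline adjustment, site and the 4-week score unused. The possible bias at the planned 10% loss is about 0 to 0.6 of 2.8 points, of either sign, and needs an arm difference in the loss rule, early pain or spread. It rests on assumed correlations of 0.3–0.7 and assumed loss models, none of which is in the documents.

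The firmer benefit is precision from baseline adjustment: power of 84–93% against about 80% at 158 per arm, given correlations of 0.8 down to 0.3 and similar baseline and one-year spread. These powers are for a comparison of means; the rank test was not evaluated.

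It would go too far to say that a repeated-measures model solves the missing-data problem. It removes bias only if loss is missing at random given the observed scores.

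**What to change.** Prespecify for Aim 1:

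1. **Primary analysis.** A mixed model for repeated measures of the PROMIS 3a scaled score at 4 weeks and 12 months in all randomized patients, with arm × visit, baseline × visit and site, and an unstructured covariance allowed to differ by arm. The primary result is the 12-month arm difference with its 95% CI.
2. **Distributional check.** A between-group rank-sum test on the one-year change. The signed rank test is a paired test and does not compare independent groups, so this wording must change in any case. The rank-sum test checks the normal model only. It cannot check missing at random, because restricting it to complete cases makes a stronger assumption about loss.
3. **Missing-not-at-random sensitivity.** A delta-adjusted analysis of the 12-month score.
4. **Reporting.** Loss by arm, set against the 4-week score.

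The cost is SAP wording and modest analysis work, with no new visits or patients. The price is reliance on missing at random and an approximately normal model. Patients with no postoperative score, and loss driven by pain arising after 4 weeks, are not rescued by the model, which is why item 3 is needed.

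### Does the Aim 2 analysis need a rule for the scan ordered when examination and patient-reported recurrence disagree?

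*Combined protocol and SAP*

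**What the plan says.** Three places in the combined protocol and SAP bear on the Aim 2 event.

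- **Outcomes to be Investigated, Specific Aim #2** gives the definition: "Hernia recurrence will be determined using the Ventral Hernia Recurrence Inventory, a validated questionnaire using patient-reported outcomes".
- **Statistical Analysis, Specific Aim 2** gives the tested quantity: "The proportion of patients in each group reporting a hernia recurrence will be examined using" Pearson's chi-square.
- **Study Design** describes how the information is gathered. The questionnaire is "a validated questionnaire that can be performed either in person or via email or phone correspondence". An examination is also planned: "At the time of the one month and one-year follow-up clinic visits, a routine physical examination will be performed on all patients". On confirmation it says: "Confirmation of a recurrent hernia will occur if the patient reports recurrence of a bulge or hernia at the site of previous repair". The next sentence has an ultrasound or CT ordered, according to the surgeon's usual practice, where the surgeon's "physical examination does not correlate with the patient-report hernia recurrence".

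Study Design also allows one-year follow-up in person or by virtual visit. For a patient who can do neither, "information will be collected through a telephone contact".

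**The concern.** The scan sentence comes directly after the sentence on confirming a recurrence, and then the text stops. It does not say whether a negative scan cancels a reported recurrence, whether a positive scan creates an event in a patient who reported none, or how a discordant patient without a scan is classified. A reader could take the scan as adjudication.

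That reading would have two consequences. If the role of the scan were decided after the counts by arm were known, the choice could move the Aim 2 result in either direction. The scan route is also not open to everyone: a patient followed by telephone has no examination and so cannot reach the disagreement that triggers imaging. Scans follow each surgeon's habit at four sites, and the document does not blind the examiner. Recurrence is also the main argument that the Introduction gives for heavier mesh, so the aim is of real interest although it is secondary.

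**Working it through.** **1. What the text fixes.** The relevant statements, side by side:

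| Place | What decides recurrence | Imaging mentioned? |
|---|---|---|
| Outcomes, Aim #2 | The questionnaire | No |
| Statistical Analysis, Aim 2 | Proportion of patients reporting | No |
| Study Design, confirmation sentence | Patient's report of a bulge or hernia | No |
| Study Design, next sentence | Not stated | Yes, per surgeon's usual practice |

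The first three agree. The fourth orders a test but names no adjudicator, reading standard or time window, and gives no rule for using the result. An analyst who follows the Statistical Analysis section counts reports. Counting adjudicated events would depart from it.

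**2. The plan's own figure.** The only stated sample size is for pain: 160 per group for 80% power at alpha 0.05. The inputs, from Power Calculation, are a difference of 10.3 − 7.5 = 2.8 and SDs of 10.9 and 6.3. The normal approximation with SD = √((10.9² + 6.3²)/2) gives 159 per group. The unequal-variance t calculation gives power of 80.0% at 160. The figure reproduces, and the Aim 2 question does not touch it. No rate, effect or power is given for Aim 2.

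**3. Could reclassification overturn a result?** The document gives no recurrence rates by arm, so the counts below are assumed. They use 176 × 0.9 ≈ 158 patients per arm and Pearson's chi-square without continuity correction.

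| Reported counts | p | Reports removed from higher arm only | p | 25% removed from both arms | p |
|---|---|---|---|---|---|
| 8 vs 24 | 0.0028 | 7 (8 vs 17) | 0.061 | 6 vs 18 | 0.011 |
| 16 vs 32 | 0.0122 | 4 (16 vs 28) | 0.051 | 12 vs 24 | 0.034 |
| 32 vs 55 | 0.0038 | 8 (32 vs 47) | 0.051 | 24 vs 41 | 0.018 |

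Significance is lost in the one-sided columns only because every reclassified patient is taken from one arm. With the same proportion removed from both arms, all three examples stay significant at 25%. At 40%, only the middle one is lost (10 vs 19, p = 0.080). Removing the same number (7, 4 or 8) from both arms makes the p-values smaller: 0.0001, 0.007 and 0.002. An example in the other direction, 16 vs 28 (p = 0.051) becoming 15 vs 28 (p = 0.033), starts so close to 0.05 that one patient is enough to cross it.

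**4. Does misreporting argue for using the scan?** With equal false reporting in both arms, the observed rate is p + (1 − p)(1 − specificity), taking sensitivity as 1. For assumed true rates of 10% vs 20% at 158 per arm, power falls from 70% at specificity 1.0 to 57% at 0.95 and 47% at 0.90. This is the price of any patient-reported endpoint. It does not raise the type I error, and stating the scan's role while keeping the report as the endpoint recovers none of it.

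**5. Would an imaging-informed analysis be better?** Assume specificity 0.90, no true difference, and scans that remove 50% of false reports in one arm and 25% in the other.

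- True rate 5%: observed rates are 5% + 95% × 10% × 50% = 9.75% and 5% + 95% × 10% × 75% = 12.1%. The chance of a significant result is 10.4%.
- True rate 20%: observed rates are 20% + 80% × 10% × 50% = 24% and 20% + 80% × 10% × 75% = 26%. The chance is 6.9%.

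Both exceed the nominal 5%. Because the scans are selective and the examiner is not stated to be blinded, unequal removal cannot be ruled out.

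**The case for a change.** The strongest opposing case is that the confirmation sentence can be read in two ways: the report is the confirmation, or the report starts a confirmation process of which the scan is the last step. On the second reading an analyst could code discordant patients by scan and cite the protocol for it. The two versions also rest on different observers. Patients learn their mesh type only at the end of the study, whereas the examination that triggers imaging is the surgeon's, and allocation takes place in the operating room. One sentence would close the matter at almost no cost.

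Part of this stands. The wording in Study Design is loose, and no sentence states what the scan result does. It does not carry over to the analysis plan, where the outcome definition and the test both count patient reports. The point about observers favours the endpoint already written, since the report is available from every contacted patient and does not depend on the surgeon's examination. A clarifying sentence would be harmless, but it would record what the plan already implies and leave the main analysis as it is.

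**Conclusion.** The observation is accurate, but it does not amount to a flaw in the analysis. This is a gap that analysts fill sensibly from the text: the Aim 2 event is the questionnaire report, and imaging is part of the surgeon's care. The endpoint is legitimate and feasible for all contact routes, and the planned comparison is sound as written. Replacing or supplementing it with scan-adjusted counts would bring in selective verification, with no assured gain.

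Aim 2 is secondary and has no stated power. The primary outcome and the 160 per group are untouched. The effect of any reclassification cannot be sized from the document, so the examples above rest wholly on assumed counts and accuracies. They show that a result is fragile mainly when reclassification is confined to one arm or p is already close to 0.05. The conclusion assumes that the Statistical Analysis section is followed as written. An analysis that let scans override reports would be a departure from the plan and should be reported as one.
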